#### **12.4.2.3 Change in the average AM reflective and AM instantaneous individual nasal symptoms from baseline to the end of each treatment week**

Similar to Section 12.4.2.2, the efficacy endpoints will be analyzed separately using a mixed model repeated measures model, adjusting for covariates that include treatment, site, baseline and week as the within-subject effect, and the model will include treatment\*week interaction term (for the FAS). The statements of a SAS PROC MIXED analysis would be:

```
proc mixed;
by individual nasal symptom;
class subject treatment site week;
model change = treatment site baseline week treatment*week;
repeated week / subject = subject type=UN;
lsmeans treatment treatment*week / cl diff e ;
ods output lsmeans=lsmeans ;
ods output diffs=diffs ;
run ; quit ;
```

For each individual symptom and each week, the adjusted means for each treatment and the estimated treatment differences for the treatment comparisons will be presented together with 95% confidence intervals for the differences and p-values for the treatment comparisons. The adjusted means and estimated treatment differences for the treatment comparisons will also be plotted, with corresponding 95% confidence intervals.

|   |   |   |
|---|---|---|
|  | STATISTICAL ANALYSIS PLAN          |   |
| Protocol Number:
GPL/CT/2014/018/III
(Study No. GSP 301-303)         | SAP Version Number:
Version 1.0 | SAP Version Date:
04-Apr-2017 |

**12.4.2.4 Change from baseline in PNSS, Overall RQLQ(S) score and RCAT at Weeks 6, 30, and 52**

RQLQ(S) (for RQLQ(S) Analysis Set), PNSS (for FAS) and RCAT (for FAS) will be analyzed separately using the same methods as described in Section 12.3.2.2 with the exception that the interaction of site-by-treatment and baseline-by-treatment will not be investigated separately in the model.

**12.4.2.5 Change from baseline in physician assessed individual nasal symptoms, individual domains of the RQLQ(S) and individual domains of the RCAT at Weeks 6, 30, and 52**

RQLQ(S) (for both the FAS and RQLQ(S) Analysis Set), PNSS (for FAS) and RCAT (for FAS) will be analyzed separately using the same methods as described in Section 12.4.2.4, with the addition of a by statement (for the individual symptoms/domains) in the SAS PROC MIXED model.

|   |   |   |
|---|---|---|
|  | STATISTICAL ANALYSIS PLAN          |   |
| Protocol Number:
GPL/CT/2014/018/III
(Study No. GSP 301-303)         | SAP Version Number:
Version 1.0 | SAP Version Date:
04-Apr-2017 |

### Appendix 1

The following shells are provided in order to provide a framework for the display of data from this study. These shells may not be reflective of every aspect of this study but are intended to show the general layout of the Tables, Listings and Figures that will be included in the final clinical study report. Tables, Listings and Figures are numbered following the ICH structure. Table headers, variables names and footnotes will be modified as needed following data analyses. Additional Tables, Listings and Figures will be generated, as needed, following the data analysis (post-hoc). All descriptive and inferential statistical analyses will be performed using SAS® statistical software Version 9.4 or later, unless otherwise noted. In general, Listings will be sorted and presented by treatment and subject number. Subject number when broken down consists of the Site Number and Subject Number.

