11.5 Treatment Visit: Visit 5 (Week 12 ±5 Days)

The following procedures and evaluations will be performed at this visit:

1. Concomitant medication evaluation
2. Focused ENT and eye examination
3. Urine pregnancy test, if applicable
4. Review instructions and provide training on the proper use of the NS
5. Collection/review of the AR Assessment Diary
6. Distribution of the AR Assessment Diary
7. Physician assessment of nasal symptom severity at the clinical site
8. Return of used double-blind study medication to the clinic
9. Prime and dispensation of double-blind study medication, as applicable
10. AE query, if applicable
11. Subject compliance check (study procedures, AR Assessment Diary, and study medication)

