Subject assessment of AR symptoms and recording and self-administration of double-blind study medication ^d		X →										
Physician assessment of nasal symptom severity		X	X	X	X	X	X	X	X	X	X	X
Review randomization criteria		X										
Randomization/treatment assignment		X										
Prime and dispensation of double-blind study medication		X	X	X	X	X	X	X	X	X	X	
Administration of double-blind study medication at the clinic ^d		X										
Return double-blind study medication to the clinic ^e			X	X	X	X	X	X	X	X	X	X
Distribution of the RQLQ(S), review instructions with the subject, and subject completion of the RQLQ(S) ^f		X		X				X				X
RCAT		X		X				X				X

Visits	Screening Visit (SV) Visit 1	Randomization Visit (RV) Visit 2	Treatment Visits (TV)									Final Visit / Discontinuation Visit (FV/DV) Visit 12
			TV 3	TV4	TV 5	TV 6	TV 7	TV 8	TV 9	TV 10	TV 11	
Week	-1	1	3	6	12	18	24	30	36	42	48	52
Day ± Window	(-7 to -10)	1	22±3	43±3	85±5	127±7	169±7	211±7	253±7	295±7	337±7	365±10
Adverse events monitoring	X	X	X	X	X	X	X	X	X	X	X	X
Subject compliance check		X	X	X	X	X	X	X	X	X	X	X

Abbreviations: AM = morning; AR = allergic rhinitis; ECG = electrocardiogram; ENT = ears, nose, and throat; HIPAA = Health Insurance Portability and Accountability Act; NS = nasal spray; RQLQ(S) = Rhinoconjunctivitis Quality of Life Questionnaire - Standardized Activities; RCAT = Rhinitis Control Assessment Test.

^a Refer to [Appendix 3](#) List of Clinical Laboratory Tests

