### **12.3.2.2 Change from baseline in the average AM iTNSS over the first 6, 30 and 52 weeks of treatment**

AM iTNSS will be analyzed using same methods as described in Section [12.3.2.1](#).

The efficacy endpoints iTNSS will be analyzed using a mixed model repeated measures model, adjusting for covariates that include treatment, site, baseline and week as the within-subject effect (for both the FAS and the PPS). The interactions of site-by-treatment and baseline-by-treatment will be investigated separately in the model and will only be included in final model if they are statistically significant at the  $\alpha=5\%$  level. An unstructured (UN) covariance will be assumed. If the model does not converge using the unstructured covariance structure, the autoregressive (order 1) AR(1) structure will be used. If this also does not converge other covariance structures deemed appropriate to fit the data will be used. This method will assume that any missing data is Missing at Random (MAR). The statements of a

|  |                                    |                                  |
|--|------------------------------------|----------------------------------|
| Protocol Number:
GPL/CT/2014/018/III
(Study No. GSP 301-303) | SAP Version Number:
Version 1.0 | SAP Version Date:
04-Apr-2017 |
|--|------------------------------------|----------------------------------|

SAS PROC MIXED analysis would be (if the interactions of treatment\*baseline and treatment\*site is not statistically significant):

```
proc mixed;
class subject treatment site week;
model change = treatment site baseline week;
repeated week / subject = subject type=UN;
lsmeans treatment / cl diff e ;
ods output lsmeans=lsmeans ;
ods output diffs=diffs ;
run ; quit ;
```

The adjusted means for each treatment and the estimated treatment differences for the treatment comparisons will be presented together with 95% confidence intervals for the differences and p-values for the treatment comparisons. The adjusted means and estimated treatment differences for the treatment comparisons will also be plotted, with corresponding 95% confidence intervals.

The responses for the first 6, 30 and 52 weeks of treatment will all be analysed in separate statistical models.

A multiple, imputation-based approach may be considered for handling missing data for AM iTNSS upon review of amount of missing data observed.

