**Table 4: Overview of Planned Efficacy Analyses for Other Efficacy Endpoints**

|   | Stats Analysis |   | Summary |   | Individual |
|---|----------------|---|---------|---|------------|
|   | T              | F | T       | F | L          |
| Change from baseline in the average AM reflective individual nasal symptoms over the first 6, 30, and 52 weeks of treatment             |                |   |         |   |            |
| MMRM – FAS  | Y              |   |         |   | Y          |
| Change from baseline in the average AM instantaneous individual nasal symptoms over the first 6, 30, and 52 weeks of treatment          |                |   |         |   |            |
| MMRM – FAS  | Y              |   |         |   | Y          |
| Change in the average AM subject-reported rTNSS and iTNSS from baseline to the end of each treatment week                               |                |   |         |   |            |
| rTNSS – MMRM – FAS  | Y              |   | Y       |   | Y          |
| rTNSS - PPS   |                |   | Y       |   |            |
| iTNSS – MMRM – FAS  | Y              |   | Y       |   | Y          |
| iTNSS - PPS   |                |   | Y       |   |            |
| Change in the average AM reflective individual nasal symptoms from baseline to the end of each treatment week                           |                |   |         |   |            |
| MMRM – FAS  | Y              |   | Y       |   | Y          |
| Change in the average AM instantaneous individual nasal symptoms from baseline to the end of each treatment week                        |                |   |         |   |            |
| MMRM – FAS  | Y              |   | Y       |   | Y          |
| Change from baseline in PNSS and physician assessed individual nasal symptoms at Weeks 6, 30, and 52                                    |                |   |         |   |            |
| MMRM – FAS  | Y              |   | Y       |   | Y          |
| Change from baseline in individual domains of the RQLQ(S) at Weeks 6, 30, and 52 for the FAS  |                |   |         |   |            |
| MMRM – FAS  | Y              |   | Y       |   | Y          |
| Change from baseline in overall RQLQ(S) score and individual domains of the RQLQ(S) at Weeks 6, 30, and 52 for the RQLQ(S) Analysis Set |                |   |         |   |            |
| MMRM – RQLQ analysis set  | Y              |   | Y       |   |            |

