**T14.1.9.1 Summary of Subject Disposition**

| Subjects                       | GSP 301 placebo
NS pH [REDACTED]
(N=xxx)
n (%) | GSP 301 placebo
NS pH [REDACTED]
(N=xxx)
n (%) | GSP 301
NS
(N=xxx)
n (%) | Total
(N=xxx)
n (%) |
|--------------------------------|---|---|-----------------------------------|---------------------------|
| Total Screened                 |   |   |                                   | xxx                       |
| Screen failures                |   |   |                                   | xxx                       |
| Treated in run-in period       |   |   |                                   | xxx                       |
| Randomized                     | xxx (xx.x)  | xxx (xx.x)  | xxx (xx.x)                        | xxx (xx.x)                |
| Randomized failures            |   |   |                                   | xxx                       |
| Terminated early               | xxx (xx.x)  | xxx (xx.x)  | xxx (xx.x)                        | xxx (xx.x)                |
| Completed study                | xxx (xx.x)  | xxx (xx.x)  | xxx (xx.x)                        | xxx (xx.x)                |
| Early Termination Reason       |   |   |                                   |                           |
| Adverse Event                  | xxx (xx.x)  | xxx (xx.x)  | xxx (xx.x)                        | xxx (xx.x)                |
| Death                          | xxx (xx.x)  | xxx (xx.x)  | xxx (xx.x)                        | xxx (xx.x)                |
| Lack of efficacy               | xxx (xx.x)  | xxx (xx.x)  | xxx (xx.x)                        | xxx (xx.x)                |
| Lost to follow-up              | xxx (xx.x)  | xxx (xx.x)  | xxx (xx.x)                        | xxx (xx.x)                |
| Non-compliance with study drug | xxx (xx.x)  | xxx (xx.x)  | xxx (xx.x)                        | xxx (xx.x)                |
| Physician Decision             | xxx (xx.x)  | xxx (xx.x)  | xxx (xx.x)                        | xxx (xx.x)                |
| Protocol Deviation             | xxx (xx.x)  | xxx (xx.x)  | xxx (xx.x)                        | xxx (xx.x)                |
| Pregnancy                      | xxx (xx.x)  | xxx (xx.x)  | xxx (xx.x)                        | xxx (xx.x)                |
| Study terminated by sponsor    | xxx (xx.x)  | xxx (xx.x)  | xxx (xx.x)                        | xxx (xx.x)                |

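### The SAP does not settle which PNSS visits enter the model; the reading that fits its shells uses three of ten and can bias the Week 30 and Week 52 differences

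*SAP*

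**What the plan says.** The schedule in Protocol Appendix 1 marks "Physician assessment of nasal symptom severity" at Visit 2 (baseline) and at each of Visits 3 to 12: Weeks 3, 6, 12, 18, 24, 30, 36, 42, 48 and 52. The visit lists agree; Protocol Section 11.5 (Week 12), for example, includes "Physician assessment of nasal symptom severity at the clinical site". RQLQ(S) and RCAT are scheduled only at Visits 2, 4, 8 and 12, so they have three post-baseline values.

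SAP Table 4 plans an MMRM on the FAS for "Change from baseline in PNSS and physician assessed individual nasal symptoms at Weeks 6, 30, and 52". Section 12.4.2.4, headed "Change from baseline in PNSS, Overall RQLQ(S) score and RCAT at Weeks 6, 30, and 52", says that RQLQ(S), PNSS and RCAT "will be analyzed separately using the same methods as described in Section 12.3.2.2", without testing the site and baseline interactions. Section 12.4.2.5 carries this over to the individual symptoms and domains. Section 12.3.2.2 is the iTNSS method. Its code has treatment, site, baseline and week, with no treatment-by-week term, and it states: "The responses for the first 6, 30 and 52 weeks of treatment will all be analysed in separate statistical models".

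Shells T14.1.9.19.2 and T14.1.9.20.2 have rows for Weeks 6, 30 and 52 only, and their footnotes describe one model with a week-by-treatment interaction. That is the form of Section 12.3.2.3 (RQLQ(S)), which places the three responses in a single model.

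**The concern.** The SAP describes two methods, and neither is a ten-visit model with visit-specific contrasts. The cited one estimates a difference averaged over a period, which is not the endpoint. The one that matches the shells conditions only on baseline and the Week 6, 30 and 52 scores. Under it, a subject who worsens between Weeks 12 and 24 and then leaves is represented by baseline and Week 6 alone, unless a discontinuation-visit score is brought in. Missing-at-random could then hold for the ten visits and fail for the three.

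This matters because heavy attrition is planned, "Lack of efficacy" is a listed early-termination reason in shell T14.1.9.1, and MAR is the only missing-data provision for PNSS. Multiple imputation is optional and named only for rTNSS and iTNSS (SAP Sections 1.0, 12.3.2.1 and 12.3.2.2).

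**Working it through.** **The plan's own figure.** SAP Section 8.0 sizes the active arm for 300 subjects at 6 months and 100 at one year. 300 / (1 - 0.25) = 400 and 100 / (1 - 0.50) = 200, so 400 meets both: 400 x 0.75 = 300 and 400 x 0.50 = 200. The figure reproduces. The PNSS contrast is 400 against 100.

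**Which visits enter.**
- Section 12.3.2.2, read literally, uses every PNSS visit up to each cut-off, but its treatment means are averages over those visits. It cannot fill the at-week rows of T14.1.9.19.2.
- Section 12.3.2.3 can fill those rows, using three visits. The other seven (Weeks 3, 12, 18, 24, 36, 42, 48) do not enter.

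**Size of the effect.** The documents give no PNSS effect, SD, correlation or dropout model, so these inputs are assumptions:
- true difference -1.0 at every visit, loosely anchored on the Phase 2 result in Protocol Section 5.4 (-1.1703, but for subject-reported rTNSS in seasonal rhinitis);
- SD 2.5;
- correlation constant at 0.5, decaying, or mixed;
- log-odds of dropout rising by 0.3 or 0.6 per PNSS point;
- pooled attrition of 25% by Week 26 and 50% by Week 52.

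The estimator was maximum likelihood for monotone missing data with unstructured covariance, arm-by-visit means and a baseline covariate. It was fitted to Weeks 6, 30 and 52 only, and to all ten visits. Large-sample runs used 500,000 subjects. Discontinuation-visit scores were not used except where stated.

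| Dropout driven by | Three visits, Week 30 | Three visits, Week 52 | All ten visits |
|---|---|---|---|
| Last observed PNSS, same rule in both arms | -0.91 to -0.98 | -0.86 to -0.97 | -0.99 to -1.01 |
| As above, true difference 0 | 0.00 to 0.02 | 0.00 to 0.02 | not run |
| Last observed PNSS, same slope, dropout rates made equal by arm | about -1.00 | about -1.00 | about -1.00 |
| Baseline or Week 6/30 scores only, or completely at random | -0.98 to -1.01 | -0.98 to -1.01 | about -1.00 |
| Last observed PNSS in one arm only | bias 0.12 to 0.24, either direction | bias 0.20 to 0.42, either direction | bias within 0.02 |

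From the first row, the loss is 1 - 0.98 = 2% to 1 - 0.91 = 9% at Week 30, and 1 - 0.97 = 3% to 1 - 0.86 = 14% at Week 52. A common rule acts unequally here because placebo scores are worse: with slope 0.6, about 47% of the active arm and 60% of placebo had left by Week 52.

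**At trial size** (1,500 trials of 400 against 100, slope 0.6), the three-visit Week 52 means were -0.85 to -0.89, a bias of at most about 0.15, with a sampling SD of 0.35 to 0.36. The ten-visit SDs were almost the same (0.34 to 0.37).

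**Two further runs.** If dropout depends on the unobserved current score (missing not at random), Week 52 is -0.78 to -0.94 with three visits and -0.86 to -0.96 with ten. If the last observed score of early leavers is counted as Week 52, the estimate is -0.98 to -1.11.

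**Model size.** An unstructured covariance has n(n + 1)/2 parameters: 3 x 4 / 2 = 6 for three visits and 10 x 11 / 2 = 55 for ten.

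**The case against.** No sentence in the SAP excludes the interim PNSS visits, and the cited Section 12.3.2.2 would keep them. The shells show which weeks are reported, not which are fitted, and Appendix 1 warns that they may not reflect every aspect of the study. PNSS by visit also appears in descriptive table T14.1.9.19.1 and in the listings. This stands: three-visit modelling is an inference from text that conflicts with itself. The cross-reference does not resolve the matter, though, because its method does not produce the required contrasts.

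A reader might infer that the last score before dropout is thrown away. The documents do not establish that. Protocol Sections 9.4 and 11.13 ask early leavers to have the Visit 12 procedures, which include PNSS. Protocol Section 13.5 says how a discontinuation score is used for RQLQ(S), with RCAT analysed similarly, but neither document says so for PNSS. A subject who leaves soon after Week 6 or Week 30 also has that last score in the three-visit model.

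It can also be said that the consequence is slight. PNSS is an other efficacy endpoint in a safety study, and SAP Section 6.0 states no hypotheses. That stands too, and it makes this a minor point.

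**Conclusion.** The point holds as a minor one. The PNSS model is specified inconsistently, and the described version that fits the outputs leaves seven of ten scheduled assessments out of the MAR conditioning. The Week 30 and Week 52 differences can then be biased if dropout depends on the omitted scores and acts unequally across arms.

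Under a common dropout rule the loss is about 2-9% at Week 30 and 3-14% at Week 52, towards no effect. At Week 52 that is less than half the sampling SD (0.15 / 0.35 = 0.43). These sizes rest wholly on the assumed effect, SD, correlation and dropout slope. The larger biases, up to 0.42 points, need dropout that tracks the score in one arm only, and nothing in the documents supports that.

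The tempting general statement, that the estimates are biased whenever worse subjects leave, is not supported. Bias was about zero with no true effect under the common rule, with completely random dropout, with equal dropout rates under a common slope, and when dropout followed only scores already in the model.

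**What to change.** In SAP Sections 12.4.2.4 and 12.4.2.5:
- Replace the reference to Section 12.3.2.2.
- For PNSS and the physician-assessed individual symptoms, fit one MMRM with all scheduled post-baseline visits (Weeks 3 to 52) and treatment-by-week, and report the Week 6, 30 and 52 contrasts.
- Assign a discontinuation-visit PNSS to a scheduled visit by its actual study day.
- Keep RQLQ(S) and RCAT at their three visits, in the Section 12.3.2.3 form, still without testing the site and baseline interactions.

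The data are already collected, and the reported rows do not change. The cost is a few sentences, a visit-window rule, and a 55-parameter covariance for about 500 subjects in the contrast, with the SAP's existing AR(1) fallback if it does not converge. AR(1) treats visits as equally spaced, which these are not, so the fallback should be used with care. The SAP already specifies an unstructured matrix for 52 weekly scores in Section 12.4.2.2 (52 x 53 / 2 = 1,378 parameters). The change reduces bias under missing-not-at-random dropout but does not remove it.

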**12.3.2.3 Change from baseline in the overall RQLQ(S) score at Weeks 6, 30, and 52**

RQLQ(S) (for the FAS) will be analyzed using similar methods as described in Section [12.3.2.1](#), with the following differences:

- Interaction of week-by-treatment will be included in the statistical model
  - Addition of week\*treatment interaction in SAS model statement
  - Week\*treatment interaction stated in SAS lsmeans statement
- The responses at 6, 30 and 52 weeks of treatment will all be analysed in the same statistical model.

The interactions of site-by-treatment and baseline-by-treatment will be investigated separately in the model and will only be included in final model if they are statistically significant at the alpha=5% level. An unstructured (UN) covariance will be assumed. If the model does not converge using the unstructured covariance structure, the autoregressive (order 1) AR(1) structure will be used. If this also does not converge other covariance structures deemed appropriate to fit the data will be used.

For each visit, the adjusted means for each treatment and the estimated treatment differences for the treatment comparisons will be presented together with 95% confidence intervals for the differences and p-values for the treatment comparisons.

|  |                                    |                                  |
|--|------------------------------------|----------------------------------|
| Protocol Number:
GPL/CT/2014/018/III
(Study No. GSP 301-303) | SAP Version Number:
Version 1.0 | SAP Version Date:
04-Apr-2017 |
|--|------------------------------------|----------------------------------|

The adjusted means and estimated treatment differences for the treatment comparisons will also be plotted, with corresponding 95% confidence intervals.

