|         | GSP 301 NS (N=xxx)                       | xxx                    | xxx.xx | xxx.xx         | xxx.xx                                 | xxx.xx             | xx.xx – xx.xx | x.xxxx  |
| Week 30 | GSP 301 placebo NS pH [REDACTED] (N=xxx) | xxx                    | xxx.xx | xxx.xx         |  |                    |               |         |
|         | GSP 301 NS (N=xxx)                       | xxx                    | xxx.xx | xxx.xx         | xxx.xx                                 | xxx.xx             | xx.xx – xx.xx | x.xxxx  |
| Week 52 | GSP 301 placebo NS pH [REDACTED] (N=xxx) | xxx                    | xxx.xx | xxx.xx         |  |                    |               |         |
|         | GSP 301 NS (N=xxx)                       | xxx                    | xxx.xx | xxx.xx         | xxx.xx                                 | xxx.xx             | xx.x – xx.x   | x.xxxx  |

Baseline is defined as the PNSS score at the randomization visit.

n: Number of subjects with data available in the specific treatment group

LSMeans: Least square means; Std Err LSMean: Standard error of the LSMean

LSMeans, Std Err of LSMean, 95% confidence intervals and p-values are based on mixed model repeated measures model with change from baseline as dependent variable, treatment group and site as fixed effect, baseline as covariate, week as the within-subject effect and week-by-treatment interaction.

Programming note: the interaction terms treatment\*baseline and treatment\*site will only be included in the footnote if significant in the model

Data source: xx

Created on: ddmmyy hh:mm

Page 1 of N

|  |                                    |                                  |
|--|------------------------------------|----------------------------------|
| Protocol Number:
GPL/CT/2014/018/III
(Study No. GSP 301-303) | SAP Version Number:
Version 1.0 | SAP Version Date:
04-Apr-2017 |
|--|------------------------------------|----------------------------------|

**T14.1.9.20.1 Summary of the Physician Assessed Individual Nasal Symptom Score  
(Full Analysis Set)  
Runny Nose**

| Treatment Group                          | Week     | Observed Data |             |        |            | Change from Baseline |             |        |            |
|--|----------|---------------|-------------|--------|------------|----------------------|-------------|--------|------------|

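### SAP 12.4.2.4 points PNSS, RCAT and RQLQ(S) (RQLQ(S) Analysis Set) to the period-average model of 12.3.2.2, so most of their results at Weeks 6, 30 and 52 would be pooled over visits

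*SAP*

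**What the plan says.** SAP 4.2 defines the PNSS, RCAT and RQLQ(S) endpoints as changes from baseline at Weeks 6, 30 and 52, and the heading of 12.4.2.4 repeats those weeks. For the method, 12.4.2.4 says these scores "will be analyzed separately using the same methods as described in Section 12.3.2.2". Its only exception is to drop the checks of two interactions, site by treatment and baseline by treatment.

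Section 12.3.2.2 is titled "Change from baseline in the average AM iTNSS over the first 6, 30 and 52 weeks of treatment". Its code is "model change = treatment site baseline week" with "lsmeans treatment / cl diff e", and it adds: "The responses for the first 6, 30 and 52 weeks of treatment will all be analysed in separate statistical models".

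The next section, 12.3.2.3, covers overall RQLQ(S) in the FAS. There, "Interaction of week-by-treatment will be included in the statistical model", the interaction also enters the lsmeans statement, and the three visits share one model.

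Section 12.4.2.5 sends physician-assessed individual symptoms, RQLQ(S) domains and RCAT domains to 12.4.2.4, adding only a by statement.

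The shells for all these endpoints have rows for Weeks 6, 30 and 52. Their footnotes give "week as the within-subject effect and week-by-treatment interaction" (T14.1.9.19.2, 20.2, 21.2, 22.2 and 23.2). T14.1.9.14.4 repeats 14.2, whose footnote says the same.

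**The concern.** A repeated-measures model with main effects for treatment and week, and no product of the two, forces the treatment difference to be equal at every visit it contains. Its estimate is a weighted average of the visit differences. That can answer a question about an average over a period, which is what iTNSS asks. It does not answer a question about the effect at a given visit unless the model contains only that visit.

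Two things are at stake. First, the secondary objective is long-term efficacy, and a pooled figure in a row labelled Week 52 would carry earlier visits with it. Second, the SAP would apply different models to one instrument. Overall RQLQ(S) in the FAS gets the interaction model, while its domains in the FAS and the overall score in the RQLQ(S) Analysis Set get the pooled model. Because the text and the shells disagree, either model could be defended after unblinding.

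**Working it through.** **Which results are pooled.** SAP Appendix 2 gives the visits. Read literally, 12.3.2.2 fits one model to each cumulative window.

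| Endpoint | First 6 weeks | First 30 weeks | First 52 weeks |
|---|---|---|---|
| RQLQ(S), RCAT | Week 6 only | Weeks 6, 30 | Weeks 6, 30, 52 |
| PNSS | Weeks 3, 6 | six visits, Weeks 3 to 30 | ten visits, Weeks 3 to 52 |

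For RQLQ(S) and RCAT the first model holds a single visit and returns the Week 6 effect exactly. Every other cell is a pooled difference.

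**Size for RQLQ(S) and RCAT.** The plan states no figure that depends on this, so the following is an illustration.

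- Retention: the SAP 8.0 planning figure of 50% attrition after 52 weeks, taken as linear. Week 6: 1 − 0.5 × 6/52 = 0.94. Week 30: 1 − 0.5 × 30/52 = 0.71. Week 52: 0.50. The same line gives 0.75 at 26 weeks, which agrees with the SAP's 25% attrition after 6 months.
- Assumed, not in the documents: unit variance; correlations of 0.6 (Weeks 6 and 30), 0.5 (Weeks 6 and 52) and 0.6 (Weeks 30 and 52); equal dropout patterns in both arms; true effects of 0.5, 0.3 and 0.1. Site and baseline are left out.

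Let p(m) be the share of subjects whose last observed visit is the m-th, and V(m) the covariance of the first m visits. The generalised least squares weights are proportional to the sum over m of p(m) · V(m)⁻¹ · 1.

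*52-week model.* The shares are 0.94 − 0.71 = 0.23, 0.71 − 0.50 = 0.21, and 0.50.

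- One visit: 0.23 × 1 = 0.230.
- Two visits: each element of V⁻¹1 is 1/1.6 = 0.625; 0.21 × 0.625 = 0.131.
- Three visits: V⁻¹1 = (0.513, 0.385, 0.513); times 0.50 gives (0.256, 0.192, 0.256).
- Sums: 0.618, 0.324, 0.256; total 1.198.
- Weights: 0.516, 0.270, 0.214.
- Reported: 0.516 × 0.5 + 0.270 × 0.3 + 0.214 × 0.1 = 0.36, where the Week 52 effect is 0.10.

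*30-week model.* The shares are 0.23 and 0.71.

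- Sums: 0.230 + 0.71 × 0.625 = 0.674, and 0.444; total 1.118.
- Weights: 0.603, 0.397.
- Reported: 0.603 × 0.5 + 0.397 × 0.3 = 0.42, where the Week 30 effect is 0.30.

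*6-week model.* Reported: 0.50, which is correct.

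**Sensitivity.**

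- Complete data, same correlations: the 52-week weights are 0.364, 0.273, 0.364 and the result is 0.30. The 30-week result is 0.40.
- Equal correlations of 0.3, 0.5 or 0.7 with the same attrition: 0.35 to 0.36 at 52 weeks and 0.42 at 30 weeks.
- Constant effect: the weights sum to 1, so there is no bias.
- Model of 12.3.2.3: run with a different assumed set (1.0, 0.5 and 0.2 in size), it returned each visit effect exactly at every correlation and retention tried.

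**PNSS.** The three-visit weights do not carry over, because more visits enter each window. In the 6-week window with complete data, assumed differences of 0.6 at Week 3 and 1.0 at Week 6 give (0.6 + 1.0)/2 = 0.8 in the row for Week 6.

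**The case against.** The best defence is that this is plainly a wrong section number. The heading of 12.4.2.4 names the three weeks. The correct method sits in the next section for the same instrument. All the shells carry the interaction and use one RQLQ(S) model for both analysis sets. Protocol 13.5 says RCAT is to be analysed much as RQLQ(S) is, and SAP 1.0 lists no departure from that. The numbering jumps from 12.3.2.3 to 12.3.6, which fits a pointer left stale by renumbering. All of this stands as evidence of intent. It does not settle what governs. Appendix 1 says that the shells may not reflect every aspect of the study and that footnotes will be changed as needed after the analyses, so the provisional part is right and the operative text is wrong.

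Some stronger readings are tempting, and the documents do not support them:

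- A reader might infer that the method can give none of the three visit effects. For RQLQ(S) and RCAT the separate 6-week model does give Week 6.
- A reader might infer that a fading effect would be reported as maintained. In the illustration the three models report 0.50, 0.42 and 0.36, which is a muted decline.
- A reader might take heavier weight on early visits as built in. It comes mainly from attrition; with complete data Weeks 6 and 52 weigh the same in the illustration.
- A reader might extend the problem to every individual symptom. Subject-reported symptoms have their own explicit models in 12.4.2.1 and 12.4.2.3.

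**Conclusion.** The point holds as an inconsistency inside the SAP. Followed literally, it changes what is estimated at Weeks 30 and 52 for PNSS, RCAT and RQLQ(S) (RQLQ(S) Analysis Set), at Week 6 for PNSS, and in the same way for the physician-assessed symptoms and the RQLQ(S) and RCAT domains.

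The distortion is nil for a constant effect and grows as the effect changes over time. In the illustration a Week 52 effect of 0.10 is reported as 0.30 with complete data and 0.36 under the planned attrition. The effects and correlations behind these figures are assumptions; only the attrition rates come from the plan.

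The reach is limited. These are other efficacy endpoints in a trial with a primary safety objective and no stated statistical hypotheses (SAP 6.0). Overall RQLQ(S) in the FAS, which is a listed secondary efficacy endpoint, already has the right model. The primary safety objective and the sample size are untouched. It should still be corrected before database lock.

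**What to change.** In SAP 12.4.2.4, change the cited section from 12.3.2.2 to 12.3.2.3, and keep the exception for the site-by-treatment and baseline-by-treatment interactions. Section 12.4.2.5 then follows without further edits, and the text, shells and endpoint definitions agree. An equivalent is to write the code out in 12.4.2.4 with `treatment*week` in both the model and lsmeans statements, as 12.4.2.2 does, and with Weeks 6, 30 and 52 in one model. The cost is one cross-reference; no data collection, shell or sample size changes.
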